2.1 General Methods

Any change made to the finalized SAP will be documented in the Clinical Study Report (CSR).

Some of the analyses detailed here may be more explicit or in some aspects different from those stated in the protocol. In case of differences, this SAP supersedes the statistical sections in the protocol.

2.1.1 Programming Conventions

The validation process will be used to confirm that all data manipulations and calculations were accurately done. Once validation is complete, a senior statistical reviewer will perform a final review of the documents to ensure the accuracy and consistency with this plan and consistency within tables. Upon completion of validation and quality review procedures, all documentation will be collected and filed by the project statistician or designee.

Analysis datasets will be mapped from eCRF data for use in table and figure production. Clinical Data Interchange Standards Consortium (CDISC) standards are not required for this Phase 4 study.

2.1.2 Reporting Conventions

The formats for the tables, listings, and figures described in this SAP will be provided in a companion document. Changes to the formats of these reports that are decided after the finalization of the SAP will not require an amendment. In addition, any additional supportive or exploratory analyses requested after SAP approval will not require amendment of the SAP. These additional analyses will be described in the CSR.

All study data from the eCRFs as well as derived variables will be provided in subject data listings. An indication of specific listings for each data type will not be indicated in the text of subsequent SAP sections. Data listings supplied as part of the CSR will be sorted by study center number concatenated with subject number, assessment dates, and/or time point.

The following conventions will be applied to all data presentations and analyses:

- Quantitative variables will generally be summarized by the number of subjects, mean, standard deviation, median, minimum, and maximum. Unless otherwise specified, the minimum and maximum values will be displayed to the same number of decimal places as the raw data, the mean and median will be presented to one extra decimal place compared to the raw data, and the standard deviation will be displayed to two extra decimal places compared to the raw data
- Categorical variables will be summarized by the number and percentage of subjects within each category. Unless otherwise specified, the percentage will be presented in parentheses to one decimal place. Frequency and percentage values of 0 will be presented as '0' rather than '0 (0)'.

- All summary tables will include the analysis population sample size (i.e. number of subjects).
- Date variables will be formatted as DDMMYYYY for presentation.

© 2007 Pearson Education, Inc.

For more information, contact the Office of the Vice President for Research and Economic Development at [contact] or [contact].

10 of 10

For more information, contact the Office of the Vice President for Research and the Office of the Vice President for Student Affairs.

For more information, contact the Office of the Vice President for Research and Economic Development at [contact] or [contact].

Digitized by [contact]

For more information, contact the Office of the Vice President for Research and Economic Development at [contact] or [contact].

For more information, contact the Office of the Vice President for Research and Economic Development at [contact] or [contact].

© 2010 Pearson Education, Inc.

For more information, contact the Office of the Vice President for Research and Economic Development at [contact] or [contact].

2.2.4 Safety Population

2.3.1. Subjective Diction

2.5.4. Subject Disposition

The disposition of subjects will be presented, including numbers of subjects who were:

- Completed,
- Withdrawn (including primary reason for withdrawal)

These numbers will also be presented by study center. The number of completed and withdrawn subjects will also be presented by visit.

2.3.2 Protocol Deviations

Subjects with any protocol deviations will be summarized by study center and overall.

Depending on the seriousness of the deviation, a subject might be excluded from the PP population, which shall be documented prior to database lock. The focus will be on major deviations which are considered to have a substantial impact on the primary efficacy outcome. Reasons for exclusion from the PP population will be presented.

[figure not shown]
2.4 Efficacy Analysis

statistical analyses will account for missing data as appropriate (SAP Section 2.4.2 below).

2.4.2 Handling of Missing Data

All analyses will be carried out based on the observed cases (OC).

2.4.3 Primary Efficacy Analysis

The primary objective of the study will be evaluated by calculating the proportion of subjects that respond "Highly satisfied" or "Satisfied" to the question [REDACTED]

[REDACTED] osed at the Month 12/early termination visit.

[REDACTED] The aim is to show that the confidence interval is above 50%, i.e. the majority of subjects are satisfied.

[REDACTED]

[REDACTED]

[REDACTED]

[REDACTED]

[REDACTED]

2.5 Safety Analysis

All safety data will be summarized descriptively based on the safety population using the Observed Cases (OC). [REDACTED]

[REDACTED]

[REDACTED]

2.5.2 Adverse Events

An overall summary of all AEs will be provided, which will include:

- number and percentage of subjects with at least one AE and number of events,
- number and percentage of subjects with at least one TEAE and number of events,
- number and percentage of subjects with at least one treatment-related TEAE and number of events,

- number and percentage of subjects with at least one mild, moderate, and severe TEAE and number of events,
- number and percentage of subjects with at least one TEAE leading to discontinuation and number of events,
- number and percentage of subjects with at least one serious TEAE and number of events.

[REDACTED]

[REDACTED]

All TEAEs by maximum intensity, serious TEAEs by maximum causality, TEAEs related to treatment by maximum intensity, TEAEs unrelated to treatment by maximum intensity, and TEAEs leading to discontinuation by maximum causality will be summarized by SOC and PT including number of subjects with at least one event, percentages, and number of events. In addition, action taken due to treatment-related TEAEs will be summarized by SOC and PT including the number of events.

For treatment-related TEAEs, the number of days to onset and duration of event will be summarized by SOC and PT.

Time to onset of an AE will be derived as the start date minus the date of most recent treatment. If the start date is missing, it will be assumed that the AE started on the day of most recent treatment.

Duration of an AE will be derived as the stop date minus the start date + 1. If the start date is missing, it will be assumed that the AE started on the day of most recent treatment. Missing stop date will not be imputed and therefore no duration will be calculated in these cases.

For subject counts, a subject will only be counted once per SOC and once per PT in cases where multiple events are reported for a subject within SOC or PT. For event counts, subjects with multiple events in a category will be counted for each event.

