3 OVERALL CLINICAL STUDY DESCRIPTION

This is a multicenter, open-label, interventional, phase 4 study to assess subject satisfaction with a twice-yearly abobotulinumtoxinA treatment regimen.

Following signature of informed consent and the screening process, eligible subjects will be treated at the baseline visit (Day 0) with abobt abobt ulinum toxinA in the glabellar region. Subjects will be re-treated at the month 6 visit,

Subjects will be monitored for up to 13 months following the initial treatment at baseline.

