8.2.1.1.5 Adverse Event Reporting Period

The clinical study period during which AEs must be reported is the period from when the subject signed the ICF to the end of the subject's participation.

The Sponsor should be informed if the Investigator becomes aware of any unusual safety information or any safety information that appears to be drug-related involving a subject who has participated in a clinical study, even after a subject has completed the clinical study.

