8.2.1.2 Reporting Procedures

8.2.1.2.1 Procedures for Reporting Adverse Events

The collection of AEs is from the time that a subject signs the ICF to their final visit.

At each post-enrollment visit, the Investigator (or sub-Investigator) will question the subject about AEs using an open non-persuasive question to elicit reporting of AEs, for example "Have you noticed any change in your health since the last visit?" Directed questioning and examination will then be performed as appropriate.

Any AE occurring during the AE reporting period, whether it is related to the study product or not, will be recorded immediately in the source document, and described on the AE form of the eCRF along with the date of onset, severity, relationship to the study product, and outcome, without omitting any requested and known information. Additional information will be requested under certain circumstances.

Adverse Events (AEs) assessed as related to the treatment or study procedure will be monitored until they have resolved or reached a stable condition. Other AEs will be monitored until the last visit if they have not resolved or reached a stable condition.

The Investigator will obtain and maintain in the subject's files all pertinent medical records, information and medical judgment from colleagues who assisted in the treatment and follow-up of the subject. If necessary, the Investigator will contact the subject's personal physician or hospital staff to obtain further details.

For SAEs (see Section 8.2.1.2.2) and pregnancies (see Section 8.2.1.2.3), the Sponsor is to be informed immediately by e-mail. The event must be reported by e-mail to the Safety Mailbox within 24 hours of receipt of the information (contact details in Section 8.2.1.2.2).

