10.1.3.1 Safety

A summary of all AEs will be provided, which will include:

- number of subjects who did not have an AE
- number of subjects with at least one AE and number of events
- number of subjects with at least one TEAE and number of events
- number of subjects with at least one related TEAE and number of events
- number of subjects with at least one TEAE by causality
- number of subjects with at least one TEAE by maximum intensity
- number of subjects with at least one TEAE leading to discontinuation
- number of subjects with at least one serious TEAE.

All TEAEs, treatment emergent SAEs, TEAEs by maximum intensity, TEAEs by causality, TEAEs by maximum intensity and causality, and TEAEs leading to discontinuation will be summarized

by SOC and PT including number of subjects with at least one event, percentages, and number of events. All related TEAEs will also be summarized by time to onset and duration.

The results of the urine pregnancy tests will be listed.

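### SAP 2.5.2 gives unresolved related TEAEs no duration, so if any occur the duration summary is biased short in its mean and possibly its maximum

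*SAP*

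**What the plan says.** Protocol 10.1.3.1 sets the scope of the summary: "All related TEAEs will also be summarized by time to onset and duration". SAP 2.5.2 carries this out: "For treatment-related TEAEs, the number of days to onset and duration of event will be summarized by SOC and PT".

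The derivation is also in SAP 2.5.2: "Duration of an AE will be derived as the stop date minus the start date + 1". Two rules for incomplete dates follow. For the start date: "If the start date is missing, it will be assumed that the AE started on the day of most recent treatment". For the stop date: "Missing stop date will not be imputed and therefore no duration will be calculated in these cases".

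On follow-up, protocol 8.2.1.2.1 says that events related to the treatment or to a study procedure "will be monitored until they have resolved or reached a stable condition"; unrelated events are followed only to the last visit. Protocol 8.2.1.1.5 defines the reporting period as "the period from when the subject signed the ICF to the end of the subject's participation". Protocol section 3 adds: "Subjects will be monitored for up to 13 months following the initial treatment at baseline".

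SAP 2.1.2 gives the default statistics for quantitative variables (number, mean, SD, median, minimum, maximum). The visible text has no method for censored durations and does not ask for a count of ongoing events beside the duration summary.

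**The concern.** A stop date can be missing for two different reasons. The event may have ended on a date nobody recorded, or it may not have ended. The SAP rule treats the two alike. In the second case the event is left out because it lasted, so the events that remain are selected on the quantity being summarised.

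The protocol's follow-up rule makes this a foreseeable case rather than a data-quality failure. A related event that has become stable without resolving has been followed correctly and still has no end date. Such an event would add nothing to the mean, median or maximum, and a reader of the duration table would not see that it was left out. For a treatment given for a temporary effect, how long related events last is information that readers will look for.

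**Working it through.** The documents give no figure for event durations or for the number of unresolved events, so there is no stated result to reproduce. The check takes the direction from the text and the size from labelled assumptions.

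**Which events drop out.** An event enters the duration statistics only if it has a stop date. I take a stop date to be the date of resolution; the visible text does not define it further. The events left out are then (a) related events that are stable but unresolved, or lost to follow-up, and (b) resolved events whose end date is unknown.

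**Direction.** Let q be the share of related events that are unresolved. The rule reports the mean of resolved events, M_res. The mean over all events is (1 − q) × M_res + q × M_unres, so the shortfall is q × (M_unres − M_res). It is zero when q = 0 and positive when unresolved events last longer on average than resolved ones. Group (b) causes no bias if the dates are missing at random: with 10% of stop dates removed at random in simulation, the mean was 23.7 days with and without them.

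**Small table.** Suppose five resolved events of 3, 5, 7, 10 and 14 days, and one ongoing at 180 days.
- SAP rule: mean 39/5 = 7.8, median 7, maximum 14.
- With the ongoing event at its minimum: mean at least 219/6 = 36.5, median 8.5, maximum at least 180.

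**Illustration consistent with follow-up to resolution or stability.** Assumptions: lognormal durations with median 14 days and log-SD 1.0, rounded up to whole days; a share q unresolved for at least 180 days; 400,000 simulated events per setting. M_res is 23.6 days. By the formula, taking unresolved events at exactly 180 days:
- q = 2%: shortfall 0.02 × 156.4 = 3.1, mean 26.7
- q = 5%: shortfall 0.05 × 156.4 = 7.8, mean 31.4
- q = 10%: shortfall 0.10 × 156.4 = 15.6, mean 39.2

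The simulation also lets a few events exceed 180 days:

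| Unresolved | Mean by SAP rule | Mean, all events (at least) | Median by SAP rule | Median, all events |
|---|---|---|---|---|
| 0% | 23.6 | 23.6 | 15 | 15 |
| 2% | 23.6 | 26.7 | 15 | 15 |
| 5% | 23.6 | 31.5 | 15 | 15 |
| 10% | 23.6 | 39.3 | 15 | 17 |

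If unresolved events are known to last only at least 30 days, the all-event mean for 2–10% unresolved is at least 23.9–24.9, a small change.

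**Upper scenario.** This applies only if stop dates after study exit are not captured. With the same duration distribution and onset 0–14 days after injection:
- 30 days of observation after injection: 32% of events have no stop date, the mean falls from 23.5 to 10.8 and the median from 15 to 10.
- 180 days of observation: 0.6% have no stop date and the mean falls from 23.6 to 22.2.

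The 30-day case corresponds at most to events after the optional month 12 re-treatment mentioned in the protocol's pregnancy test section, given the 13-month limit.

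**The case against.** The strongest reply is that the protocol already limits the problem. Related events are exactly those followed beyond the last visit if need be, so most events open at study exit should later receive a stop date. This stands, and it confines the loss mainly to persistent or lost-to-follow-up events. It does not remove the loss, because stability without resolution is a permitted end of follow-up. The documents also do not say whether a stop date after exit reaches the eCRF, since collection of adverse events ends with participation.

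A reader might infer that a third or more of related events would be dropped. The documents do not support that. It requires every event to be cut off about 30 days after injection, whereas the visible SOC and PT summary is not split by injection and also takes in events after the baseline and month 6 treatments, which have much longer observation.

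A reader might also infer that unresolved events are hidden from the report. They are not. They count in the related-TEAE tables by SOC and PT, outcome is recorded on the AE form (protocol 8.2.1.2.1), and SAP 2.1.2 lists all eCRF data and derived variables.

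Three further points stand. Duration is not among the adverse-event endpoints in SAP 1.6, nor in the safety endpoint of protocol 2.1.3 (incidence and severity). The start-date rule can lengthen some durations, which works the other way. Parts of SAP 2.5 and 2.5.2 are redacted and table formats sit in a companion document, so a count of ongoing events may already be planned there; the visible stop-date rule is nevertheless explicit.

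**Conclusion.** The concern holds, conditionally and at minor severity. If any related TEAE is unresolved at last contact, SAP 2.5.2 removes it from the duration statistics, and the summary no longer covers all related TEAEs as protocol 10.1.3.1 says. The mean is then biased short on average. The maximum is too short only if an ongoing event has outlasted the longest resolved one. If all related TEAEs resolve with recorded stop dates, nothing changes.

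The size cannot be fixed from the documents. With 2–10% of related events unresolved for at least 180 days, the reported mean is about 24 days against at least 27–39, and the median moves by 0–2 days. These figures rest on the assumed lognormal durations, the unresolved share and the 180-day minimum. It would go too far to say that the plan will report durations that are too short, or that the events left out are always the longest: the first depends on unresolved events occurring, and the second holds on average only. The summary is descriptive and the primary endpoint is not affected.

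**What to change.** In SAP 2.5.2:

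- Separate events that are ongoing or unresolved at last contact from resolved events with an unknown stop date, using the recorded AE outcome. The no-imputation rule can stay for the latter.
- For the former, derive a censored duration: last contact date − start date + 1.
- In the duration table, show the number resolved and the number ongoing for each SOC and PT.
- Mark censored values with '+' in the minimum and maximum.
- Label the mean and median as resolved events only.

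A Kaplan-Meier median is optional where counts allow. It should not be mandatory by PT, where events may be few and a subject may contribute more than one.

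The cost is a few lines of SAP text and minor programming on data already collected. The downside is that reported durations may look longer. If no related event is ongoing, only the labels and counts change.

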2.5.3 Other Safety Assessments

The numbers and percentages of subjects with abnormalities in focused physical examination will be summarized. The results of the urine pregnancy tests will only be listed.

2.8 Changes in the Analysis Planned in the Protocol

There are no significant changes to the analysis planned in the protocol.

3 Reference List

There are no other references beyond those that are included in the protocol.
